**9/27/19**

### **STATEMENT OF COMPLIANCE**

The study will be conducted in accordance with the International Conference on Helsinki guidelines for Good Clinical Practice (ICH E6), and the Code of Federal Regulations on the Protection of Human Subjects (45 CFR Part 46). All personnel involved in the conduct of this study have completed human subjects' protection training.

## LIST OF ABBREVIATIONS

AC	Active Control
CE	Capsule Endoscopy (Risk Assessment)
CERA	Capsule Endoscopy Risk Assessment
CFR	Code of Federal Regulations
CHEER	Capsule Endoscopy for HEmorrhage in the ER
CORE	Central Reading Group for Endoscopy
ED	Emergency Department
EGD	Esophagogastroduodenoscopy
GBS	Glasgow Blatchford Score
GI	Gastrointestinal
ICH	International Conference on Harmonization
IRB	Institutional Review Board
NIH	National Institutes of Health
RC	Research Coordinator
ST	Standard (Risk Assessment)
UGIB	Upper GI Bleed
US	United States
VCE	Video Capsule Endoscopy

## PROTOCOL SUMMARY

Title:	Capsule Endoscopy for HEmorrhage in the ER (CHEER)
Précis:	This is a multi-center randomized controlled trial examining the use of Video Capsule Endoscopy (VCE) to discharge low-moderate risk patients with suspected upper gastrointestinal bleeds (UGIB) from the Emergency Department (ED.) We will enroll 100 subjects at 4 sites who present with signs of hemodynamically stable UGIBs and compare VCE risk assessment to an Active Control (AC) group who receive inpatient upper endoscopy (EGD).
Objectives:	
Primary: Our primary goal is to determine whether ED VCE is able to discharge low risk patients for outpatient management of upper GI bleeds.
 
Secondary: Our secondary objective is to estimate the sensitivity and specificity of VCE compared to subsequent EGD in the detection of serious bleeding lesions in the upper gastrointestinal (GI) tract.
 
Sample size is 100 patients, age <math>\geq</math> 18 in 4 urban EDs, mixed gender, mixed race, hemodynamically stable with possible co-morbidities.

Population:	Study subjects will be enrolled from larger pool of adult ED patients presenting with acute overt UGIB defined as bloody emesis and/or coffee ground vomiting and/or melena within the previous 48 hours.
Number of Sites:	4
Study Duration:	12 months
Subject Participation Duration:	30 days
Estimated Time to Complete Enrollment:	1 year

## 2 INTRODUCTION: BACKGROUND INFORMATION AND SCIENTIFIC RATIONALE

### 2.1 Background Information

Upper gastrointestinal (GI) hemorrhage is the primary diagnosis for 300,000 annual Emergency Department (ED) admissions in the US. The challenge for the ED is to determine whether a patient with a suspected upper GI bleed (UGIB) needs urgent intervention (i.e. hospital admission for endoscopy, surgery and/or transfusion) or can be safely discharged for outpatient management. The Glasgow-Blatchford Score (GBS) was developed to identify GI bleeds that require hospital admission and urgent intervention. The GBS has a high sensitivity but low specificity. For high risk bleeds, standard of care is hospital admission and a performance of esophagogastroduodenoscopy (upper endoscopy or EGD) within 24 hours. However, many US hospitals do not have the resources to perform EGD on all patients suspected to have UGIB within 24 hours of admission. As a result, a significant proportion of patients with low-risk bleeds are admitted to the hospital for observation and may never receive EGD and many patients with high-risk lesions receive delayed care because of the inability to discriminate low risk from high risk bleeding events.

Video capsule endoscopy (VCE) was initially approved in 2001 by the Food and Drug Administration as a noninvasive diagnostic test for occult UGIB. This technology represented a significant advance in the investigation of intestinal diseases. Indications that have been validated include cryptogenic gastrointestinal bleeding, familial polyposis, and intestinal lesions in patients with Crohn's disease. Based on recent evidence, VCE represents a novel strategy to perform rapid diagnosis of suspected UGIB, portal hypertension, non-cardiac chest pain, gastroesophageal reflux disease in the emergency department (ED). There are limited numbers of EDs in the United States that have used VCE on trial- and protocol-based patient studies, but the results are encouraging. Given the expanding role of advanced diagnostic and point-of-care testing in US EDs, VCE has great potential for future evaluation of ED gastrointestinal complaints.

VCE offers potential advantages over traditional EGD including the ability to be performed 24 hours a day without sedation and interpreted at the bedside by emergency physicians. In addition, VCE is much less invasive, is painless, and enables the patient to pursue normal daily activities after the procedure. ED physicians may use the information to make real-time decisions regarding the need for hospitalization, endoscopic hemostasis, and risk stratification. Real-time imaging has been shown to be helpful in early diagnosis of bleeding lesions [1], and the videos generated can be sent to an off-site specialist for an over-read after the initial ED interpretation. This workflow is similar to that of many current ED diagnostic tests such as electrocardiograms and radiology examinations. This ability to transmit images could become especially important in rural communities or in communities that have limited access to a gastroenterologist. Incorporation of VCE into ED practice could follow a trajectory similar to that of point-of-care ultrasonography, an imaging modality in which ED physicians have become increasingly skilled and for which indications continue to expand [2].

In patients requiring VCE, most contraindications are relative and the procedure has been performed safely in a variety of clinical settings [3]. Pacemakers and other electrical medical

devices are not a contra- indication to the procedure with newer versions of the capsules. The only absolute contraindications are bowel obstruction and pregnancy [4]. There is a low risk of non-natural excretion of the capsule estimated at less than 1 in 100 [5]. In general, the procedure poses significantly less risk than traditional EGD, and multiple studies have shown that VCE is well tolerated in ED patients with suspected acute UGIB [6-8].

The American Society of Gastrointestinal Endoscopy states that credentials for VCE should be determined independently from other endoscopic procedures such as colonoscopy, sigmoidoscopy, or any other endoscopic procedure [9]. The American Society of Gastrointestinal Endoscopy emphasizes sound medical training, appropriate patient selection, correct interpretation, and continued medical management for all patients. VCE requires only image interpretation and does not require procedural skill training associated with other endoscopic procedures; therefore, ED physicians can meet these criteria with basic training.

In a study of 25 subjects, VCE interpretation by emergency physicians demonstrated excellent agreement with gastroenterologists for the presence of fresh or coffee-ground blood (0.96 overall agreement;  $\kappa \geq 0.90$ ) [7]. In another study, 126 emergency physicians were asked to look at standardized videos from ED patients who presented with acute UGIB. Compared with expert gastroenterology-adjudicated interpretation, the sensitivity of ED physicians to detect blood was 0.94% (95% CI: 91%-96%) and specificity was 87% (95% CI: 80%-92%) [10].

Gastrointestinal hemorrhage is a common emergency condition, and the severity ranges from benign to life threatening. Risk stratification of acute UGIB is challenging in the ED because traditional diagnostic approach using the physical exam, lab testing and radiographic studies is too nonspecific to be used without adjunctive endoscopy. As a result, many patients with an ultimately benign clinical course are admitted to the hospital and incur considerable costs. Without an ED-based endoscopy, alternative means to risk stratify patients with signs of UGIB include performing nasogastric aspiration, which is uncomfortable for patients [11], using clinical decision rules, such as the Rockall Risk Score and Glasgow-Blatchford Score, or admitting all patients with suspected upper gastrointestinal bleed for endoscopy [12].

Most endoscopy capsules are manufactured for use in the small bowel, but the esophageal capsule endoscope (PillCam UGI, Medtronic) is designed to visualize the upper gastrointestinal tract. The esophageal VCE is equipped with 2 cameras at either end that take 35 pictures per second for 30 minutes. Initial studies with early-generation esophageal VCE demonstrated a sensitivity of 92% and specificity of 95% to diagnose chronic reflux esophagitis [13]. In addition, the sensitivity and the specificity were found to be 97% and 99%, respectively, for the diagnosis of Barrett esophagus and 89% and 99%, respectively, for diagnosis of esophagitis [13].

The use of esophageal VCE in the ED to directly visualize the upper gastrointestinal tract and identify presence or absence of blood is a novel approach that has been studied in 4 ED-based studies. First, Rubin et al [14] studied 24 patients who presented to the ED with signs of UGIB. In this study, patients were randomized to either receive a VCE in the ED with real-time interpretation or receive standard care. Of the 12 patients in the experimental group, 7 had

bleeding detected on VCE and all had bleeding confirmed with subsequent EGD within 6 hours of hospital admission. Of the 4 patients who had a negative result on VCE (1 could not tolerate a VCE), all 4 had subsequent negative findings on EGD. On average, patients in the experimental group had an EGD performed sooner than the control group, but there was no change in clinical outcomes.

Gralnek et al [6] studied 41 patients who presented to the ED with UGIB and each received both a nasogastric tube and VCE. All patients had an EGD performed in the hospital within 12-24 hours after presentation. Of the 41 patients, 18 had blood in the upper gastrointestinal tract detected by EGD; capsule endoscopy detected blood in 83% (15/18) of these cases compared with a nasogastric aspiration, which detected blood in 33.3% (6/18). It is important to note that in 9 of these patients, the capsule detected blood in the duodenum, when nasogastric aspiration was reported to be either clear or bilious. Lack of detection of post-pyloric bleeding is an important limitation of nasogastric aspiration. Patients preferred VCE over nasogastric aspiration.

A third study conducted in the ED on the use of VCE enrolled 25 subjects with acute upper gastrointestinal hemorrhage [7]. In this study, [name] et al demonstrated an 88% sensitivity (95% CI: 65%- 100%) and 64% specificity (95% CI: 35%-92%) for the detection of fresh blood compared with an EGD performed with 24 hours. Capsule endoscopy missed a bleeding lesion located in the post- pyloric region, which was not imaged because of expired battery life (30 minutes).

Most recently, the use of esophageal VCE in the ED was compared with the validated triage system, the Glasgow-Blatchford Score, to identify the number of patients who may be suitable for outpatient care [8]. Patients who presented to the ED for suspected acute UGIB were enrolled and administered esophageal VCE. For capsules that passed the pylorus and reached the duodenum, high-risk lesions were detected with a 95% sensitivity (95% CI: 72%-100%) and a 92% specificity (95% CI: 73%- 99%) compared with the Blatchford Score that demonstrated a 94% sensitivity (95% CI: 72%-100%) and a 16% specificity (95% CI: 5%-37%).

There has been one feasibility study published to test whether VCE can reduce hospital admissions in patients with suspected UGIB. In a prospective randomized controlled trial in which patients who presented with symptoms or signs suggestive of UGIB were randomized to receive either the standard treatment of hospital management versus VCE. Patients were also graded by Glasgow Blatchford score (GBS) at the ED for assessment of need of hospital admission. In this study, seventy-one patients fulfilled the recruitment criteria, with 37 subjects randomized to the VCE group and 34 subjects randomized to standard group. Seven VCE patients with active bleeding or significant endoscopic findings were admitted to the hospital compared with the standard group in which all 34 patients were admitted. There was no difference in the clinical outcome in terms of recurrent bleeding and 30-day mortality. In addition, hospital admission was also greatly reduced if VCE results were used instead of the GBS to determine whether patients were admitted or managed in the outpatient setting.[9]

In all ED studies that have been conducted for acute upper gastrointestinal hemorrhage, VCE has performed well when it travels through the pylorus. However, several high-risk lesions were missed if the VCE did not travel through the pylorus before the battery expired. The time to pass the pylorus is variable. At 60 minutes, 98% of capsules visualize the duodenum [6]; when the battery life is only approximately 20-30 minutes, approximately 50% visualize the duodenum (12/25 [7], 44/83 [8], and 7/12 [14]). In one study, the single missed active bleeding occurred in a patient who was bleeding in the post-pyloric duodenum and in whom the VCE battery expired before reaching the post-pyloric region [7]. For standard EGD, the use of pro-kinetic agents such as erythromycin or metoclopramide has improved mucosal visualization and has been increasingly used before the procedure. This strategy, combined with 60 minutes of visualization, will likely increase the accuracy of VCE as well.

The cost of the VCE is an important factor that affects future use in the ED. The physician Medicare national average fee is \$705 for the PillCam UGI and \$50 for the professional fee. Although expensive, VCE may be cost-effective if it safely reduces hospital admissions or emergency EGD. For comparison, in 2011, 236,000 patients received an EGD (International Classification of Diseases, Ninth Revision code 45.13) in the hospital for an upper UGIB, the median length of stay was 4.0 days, and the median charges were \$23,549.17 [12].

A decision-analytic model showed that VCE is cost effective for low- to moderate-risk patients despite increased upfront costs compared with clinical decision rules or nasogastric tubes. The use of VCE in the ED can potentially lead to more patients being safely discharged from the ED. The hospital admission is the single most expensive decision made by an emergency physician. Chandran et al [8] showed that the higher sensitivity of VCE compared with the Glasgow-Blatchford Score would have saved \$1691 per VCE by increasing the number of patients who could receive an outpatient EGD.

Currently, the VCE does not replace the need for traditional EGD when hemostasis or biopsy is needed. Technological advancements may allow a VCE operator to control movement of the capsule, collect biopsy samples, and perform therapeutic functions.

## **2.2 Rationale**

We believe there is an opportunity to improve the risk stratification of acute UGIB that presents to the Emergency Department through the use of Video Capsule Endoscopy. Our primary hypothesis is that VCE allows for safe outpatient management of ED patients with suspected upper GI hemorrhage. A multicenter randomized control trial is proposed to investigate the safety of this diagnostic modality.

## **2.3 Potential Risks and Benefits**

### **2.3.1 Potential Risks**

Patients for whom study enrollment may interfere with standard clinical care will not be enrolled. Alternatives to study participation are for patient to receive standard of care treatment for UGIB.

We have considered a variety of potential risks to participants including cognitive, affective, physical, legal/confidentiality and economic risks. The PillCam UGI is manufactured by Medtronic and has been FDA approved with a robust published safety profile since approval in 2004.

The physical risks associated with the PillCam are generally related to potential non-natural excretion. There is a small risk that the capsule could become stuck in the stomach or bowel. Based on published and unpublished data, the PillCam Small Bowel (SB) capsule has been reported to be retained in the GI tract for periods of at least 23 months without adverse events. The capsule has been shown to remain intact, without symptoms, for months. In fact, a large retrospective review by Chaifetz, et al. found that a retained capsule often leads to a diagnosis. Furthermore, the device is made of biocompatible materials and its internal parts are non-toxic. The incidence of capsule retention has been reported to be less than 1% but this figure may be higher in Crohn's disease or other conditions. The rate of surgical removal was noted to be 0.75% (Barkun JS, Friedman S. Am J Gastroenterol 2002; 97:A83).

Surgery may be required to remove a retained capsule. In general, if a patient does not pass the PillCam naturally through the upper GI tract due to gastroparesis, an EGD will be sufficient to retrieve the capsule. Given that most patients will receive an EGD as part of their standard work-up for the disease, this does not pose a significant increased risk. Patients who are at increased risk of capsule retention are not appropriate study subjects including people with swallowing disorders or with known or suspected gastrointestinal obstructions, strictures or fistulas.

Pregnant women will not be included.

Also, people with cardiac pacemakers or other implanted electro-medical devices will not be given the PillCam given a theoretical risk that the devices could interact.

Patients will be advised not to have an MRI for 30 days and to consult with their doctor prior to receiving an MRI in the future. For patients who are unsure whether they excreted the PillCam, *an abdominal X-Ray may be required as an outpatient to confirm passage.*

In order to maximize safety for all study subjects, only consented and enrolled subjects will be administered the PillCam under the personal supervision of the PI or under the supervision of a sub-investigator/trained research associate responsible to the PI. In addition, the PillCam will be stored in a secure, limited access area. Product accountability log must include the protocol number, investigative site name, product name, medical units (i.e., video capsules), serial number and subject ID number.

We anticipate low cognitive risk to participants. Diagnosis of source of gastrointestinal bleeding lesion is presumably one of the reasons the patient presented for emergency care. We do not anticipate an affective risk to participants. Some participants may be bothered by the knowledge that the device will pass naturally and may take several days to be excreted.

We believe the study poses a low privacy risk to subjects as all data will be encrypted and no PHI will be stored with data.

Finally, the study has a low economic risk since the device and the interpretation of the device are not being billed to the subject or his/her insurance company. *The only economic risk may result from an unanticipated complication of the device that will not be covered by Medtronic, LTD, the manufacturer of the pill camera, GWUH or MFA.*

Minor adverse events that occur will be reported directly to the principal investigator and overall study coordinator at the next business day. Minor adverse events include inability to tolerate capsule, discomfort swallowing capsule, issues regarding video capture, issues regarding video transmission, erroneous video interpretation that has no significant impact on clinical care, protocol deviations, reactions to medication (pro-motility agent), delays in endoscopy interpretation, delays in EGD and others. All minor adverse events will be shared with the entire research team at regularly scheduled monthly calls or sooner at the PI's discretion.

Any major adverse events that occur will be reported directly to the principal investigator who will be available to study subjects 24 hours a day. Severe adverse events will be reported to the entire research team, the DSMB and to IRB within 24 hours. Updates will be provided after a full investigation is completed. Since the PillCam is an FDA-approved device and not an experimental device, all SAE's will also be reported to the FDA. Potential major adverse events include missed high-risk lesions, delayed definitive care, patients who are discharged from hospital and experience a major outcome (see below), capsule retention in the small bowel, and any serious outcome that may be related to study protocol. A DSMB will be formed that includes experts in emergency medicine, gastroenterology and research methodology. DSMB will meet annually during which a report will be produced by PI and as needed for SAE's.

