**4.4 Study procedure:**

1. Screen potential patients with signs of upper GI bleeding (melena, h/o hematemesis or coffee-ground emesis) from general pool of ED patients. (Form used, *CHEER:1*)
2. Patients who screen as eligible will be approached about potential interest, to review of inclusion and exclusion criteria, and obtain informed consent. (*See below for full list of inclusion/ exclusion criteria.*)
3. Research Coordinator will calculate traditional risk stratification scores (Glasgow – Blatchford and Rockall).
4. All consented patients will be given a study ID and recorded in enrollment log. (Form used, *CHEER:2*)
5. Once enrolled, all subjects will be randomized to either Active Control (AC) [admission plus EGD within hospital stay] or experimental Capsule Endoscopy Risk Assessment (CERA) in ED.
6. Only patients randomized to the experimental arm will receive video capsule endoscopy in the emergency department. 20 to 60 minutes before capsule ingestion, each patient in the experimental arm receives a single dose of intravenous metoclopramide 10 mg (or erythromycin 500mg intravenously if there is a contraindication), which helps to promote gastric motility and improves visualization of the gastric mucosa at endoscopy. The Research Coordinator (RC) will prepare the patient for VCE. (*See below for description of procedure.*)
7. Within 2 hours of presenting to the ED, patient will ingest video capsule-- RC will monitor progress on real-time viewer for passage through pylorus. Upon passing the pylorus, we will record 5 more minutes of video or until battery runs out – whichever occurs first.
8. Patient data will be completed using a standardized data collection tool including the following elements: chief complaint of patient, history of present illness, past medical history, pertinent lab findings, current medications, vital signs, focused physical exam findings and all relevant treatments administered during the ED and hospital stay. (Form Used, *CHEER:3*)

9. At completion of VCE, patient satisfaction regarding VCE will be assessed in patients in the experimental group. (Form used, *CHEER*: 4)
10. For Active Control (AC) group each patient will be admitted.

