### 5.2 Subject Exclusion Criteria

1. Upper GI Bleed with hemodynamic instability (BP<90 mmHg, pulse>120 beats per minute, and Hgb < 9 g/dL)
2. High Risk Upper GI Bleed (Glasgow Blatchford Score\*  $\geq$  6)
3. Signs, symptoms or history of liver cirrhosis or liver failure
4. Signs, symptoms or history of decompensated heart failure or congestive heart failure
5. Presumed Pregnant, trying to conceive or breastfeeding
6. Known history of gastric cancer
7. Known history of gastric or esophageal varices
8. GI surgery within the last 6 months
9. Prior enrollment in the CHEER Study
10. Prisoner or Ward of State
11. Trouble swallowing, suspected bowel obstruction or perforation, per treating clinician
12. Past UGI tract surgery (e.g., Bilroth I or II, esophagectomy, gastrectomy, bariatric procedure) that changes Gastrointestinal anatomy
13. Known history of gastroparesis, esophageal stricture or Crohn’s disease
14. Altered mental status that limits the ability to swallow a capsule
15. Expected to have Magnetic Resonance Imaging (MRI) examination within 7 days
16. Consumed medications within the past 12 hours that may coat the upper GI tract such as antacids or sucralfate or Maalox and potentially limits capsule visualization
17. Patient either refuses or is unable to get traditional EGD
18. Patient does not have reliable contact information – no phone, no permanent address
19. Patient refuses
20. Unable to provide written consent
21. Non-English speaker
22. Suspected middle or lower GI bleeding
23. Treating ED Physician is not amenable to admission or discharge based on randomization or Video Capsule Endoscopy results.

\* As a modification, the GBS Score modified from the traditional GBS score to reduce the Hemoglobin cut-off for 6 points from 10g/dL to 9 g/dL (see Appendix B, CHEER 4; patient screening)

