## **7 STUDY PROCEDURES**

### **7.1 Screening and Randomization**

Potential study subjects will be identified while present in the Emergency Department. While the patient is in the ED, a member of the research team will be notified. This researcher will determine if the patient meets the inclusion and exclusion criteria. If the patient meets enrollment criteria, the study protocol will be explained to the patient. If they express interest in participation, informed consent will be obtained, randomization will take place, study procedures followed, and follow-up with GI for EGD will be arranged before the patient is discharged from the ED.

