### **8.3 Cheer 3: Patient Data Collection Form**

Patient data collection form is completed for all randomized patients. This form includes detailed medical data obtained during screening for the study.

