**13. Trouble swallowing, suspected bowel obstruction or perforation, per treating clinician**

Yes No (Must be NO to be eligible for study)

**14. Past UGI tract surgery (e.g., Billroth I or II, esophagectomy, gastrectomy, bariatric procedure) that changes Gastrointestinal anatomy**

Yes No (Must be NO to be eligible for study)

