#### **Do you have any of the following medical problems?**

Heart attack OR Heart disease	Ulcer or Gastritis or Acid Reflux
Diabetes Mellitus	Hemorrhoids
Cancer that spread	Prior abdominal surgery OR pelvic surgery
Kidney Failure OR on dialysis	inflammatory bowel disease (Crohn's OR Ulcerative Colitis)
Previous Smoker OR Active Smoker	Bowel Obstruction
Liver Disease OR Liver Cirrhosis	Other: _____

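### The risk section bars the capsule for people with implanted electro-medical devices and calls people with GI fistulas unsuitable, but neither the exclusion list nor the screening form mentions them

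*Combined protocol and SAP*

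**What the plan says.** Section 2.3.1 (Potential Risks) sets two rules. On devices, "people with cardiac pacemakers or other implanted electro-medical devices will not be given the PillCam given a theoretical risk that the devices could interact". On capsule retention, it lists as unsuitable for the study people with swallowing disorders or with "known or suspected gastrointestinal obstructions, strictures or fistulas".

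Section 2.1 (Background Information) takes the opposite line on devices: with newer capsules, pacemakers and other electrical devices are said not to be a contraindication.

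The gate to the trial is in Section 7.1: "This researcher will determine if the patient meets the inclusion and exclusion criteria". Section 4.4 then follows with "Once enrolled, all subjects will be randomized to either Active Control (AC" arm or the capsule (CERA) arm. The nearest entries in Section 5.2 and on the screening form (18.4) are "Trouble swallowing, suspected bowel obstruction or perforation, per treating clinician" and "Known history of gastroparesis, esophageal stricture", the latter continuing to Crohn's disease.

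**The concern.** A rule about who may swallow the capsule protects patients only if it is applied before the capsule is given. It protects the randomised comparison only if it is applied before allocation. Here the rules stand in the risk narrative and are absent from the criteria that decide enrolment.

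A person with a pacemaker, a neurostimulator or a GI fistula can therefore satisfy every listed criterion and be randomised to CERA. Two things can follow:

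- **Not noticed.** The person receives a capsule that Section 2.3.1 says they will not receive or, with a fistula, enters a trial for which that section calls them unsuitable. The same section says a retained capsule may need surgery to remove.
- **Noticed after allocation.** The capsule is withheld, which can happen only in the CERA arm. The protocol gives no rule for managing or analysing that subject.

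**Working it through.** **Step 1. Set the risk section against the two lists.**

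| Named in 2.3.1 | Section 5.2 (23 exclusions) | Screening form 18.4 (25 items) |
|---|---|---|
| Pregnancy | No. 5 | Yes |
| Swallowing disorder | No. 11 | Item 13 |
| GI obstruction | No. 11 (suspected) | Item 13 (suspected) |
| GI stricture | No. 13: known esophageal only | Item 15: known esophageal only |
| GI fistula | None | None |
| Implanted electro-medical device | None | None |

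The form is numbered 1 to 24 with number 5 used twice, which gives 25 items.

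**Step 2. Look for indirect coverage.**

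- Exclusion 4 (heart failure) removes some cardiac device wearers. The Glasgow-Blatchford form gives 2 points for cardiac disease, but 2 points alone do not reach the exclusion threshold of 6. Neither touches non-cardiac devices.
- Exclusion 15 concerns an MRI expected within 7 days, not a device.
- Exclusions 8 (recent GI surgery), 11, 12 (anatomy-altering surgery) and 13 (which includes Crohn's disease) cover related retention risks. What remains is fistula without those conditions, and stricture that is non-esophageal or only suspected, again without them.
- Exclusion 23 concerns whether the physician accepts the disposition, not capsule safety.
- The checklist in 18.5 that asks "Do you have any of the following medical problems" names 11 conditions, none of them a device, stricture or fistula. It has a free-text field for other conditions. Section 8.3 says "Patient data collection form is completed for all randomized patients", using data obtained during screening. The form records history and sets no eligibility rule.

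**Step 3. How many subjects.** The documents give no device prevalence, so *p* is assumed to lie between 0.5% and 5% of randomised subjects. The allocation ratio is also not stated; 1:1 is assumed, giving 50 of the 100 subjects in CERA.

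Expected number = 50 × *p*. Chance of at least one = 1 − (1 − *p*)^50.

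| *p* | Expected in CERA | Chance of at least one |
|---|---|---|
| 0.5% | 0.25 | 22.2% |
| 2% | 1.0 | 63.6% |
| 5% | 2.5 | 92.3% |

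No comparable range is offered for fistulas or the uncovered strictures.

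**Step 4. Effect on the primary comparison.** Section 11.2 claims at least 80% power for a 25-point difference in admission among low-risk subjects, with all controls admitted. With 100 subjects at 1:1 and 20% high risk, there are 50 × 0.8 = 40 low-risk subjects per arm. With 0 of 40 controls discharged, a two-sided Fisher test at 0.05 needs at least 6 of 40 CERA discharges (p = 0.026 at 6, p = 0.055 at 5). If *b* CERA subjects cannot be discharged because the capsule is withheld, and they stay in the denominator, then power = P(X ≥ 6) with X ~ Binomial(40 − *b*, 0.25):

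| *b* | Power |
|---|---|
| 0 | 95.7% |
| 1 | 94.9% |
| 2 | 94.0% |
| 3 | 92.9% |

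The plan's claim of at least 80% is met in every row.

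**The case against.** The strongest reply is that, for devices, the exclusion list may be right and the risk section out of date. Section 2.1 says devices are not a contraindication with newer capsules and names bowel obstruction and pregnancy as the only absolute ones. Section 5.2 covers pregnancy and suspected obstruction, and 2.3.1 itself calls the device risk theoretical. This stands as a reason not to claim demonstrated harm. It does not remove the inconsistency: the protocol holds both positions, the criteria settle neither, and the documents do not show that the Section 2.1 statement applies to the PillCam UGI.

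Second, the device sentence governs giving the capsule, not enrolment. It binds staff as protocol text, capsules are given only under supervision (2.3.1), and medical history is taken at screening (7.4). Staff may well notice. But no criterion makes the person ineligible, so the rule can first take effect after allocation, where its handling is undefined.

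Third, the fistula and stricture gap is narrow, because most of the retention risks in 2.3.1 reached the exclusion list. That is correct and limits the weight of this part.

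Fourth, the prevalence range is assumed and wide, and 25% is a minimum detectable difference. In the earlier randomised trial described in 2.1, 7 of 37 capsule patients were admitted, which is 30/37 = 81% not admitted. At that rate, power is essentially 100% with or without three blocked subjects. This supports the view that the efficacy comparison is not at risk.

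**Conclusion.** The concern holds. Two safety restrictions in Section 2.3.1 are missing from the criteria and the form that decide enrolment, and a third, on strictures, is carried over only in part. Followed as written, the plan can randomise to the capsule arm a person whom its own risk section rules out.

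The size is modest. Under the assumed 0.5% to 5% device prevalence and 50 CERA subjects, between 0.25 and 2.5 such subjects are expected; exclusion 4 and the cardiac points in the Glasgow-Blatchford score probably push this towards the lower end. Even three blocked subjects cost less than 3 points of power (95.7% to 92.9%). The case for change rests on patient safety, on consistency within the protocol, and on avoiding one-sided withholding after randomisation.

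**What to change.** 1. **Devices.** Add cardiac pacemaker or other implanted electro-medical device to Section 5.2 and to the screening form, checked before randomisation. Alternatively, if the Section 2.1 statement on newer capsules is confirmed for the PillCam UGI, delete the bar from 2.3.1. Either way, 2.1, 2.3.1 and 5.2 should then agree.
2. **Strictures and fistulas.** Add any known or suspected GI stricture or fistula to Section 5.2 and the screening form.

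The cost is a short amendment, two screening-form items and a few more screen failures. The sample size and the analysis do not change.
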